b) Vascular endothelial cell protein expression: These procedures have been described in detail previously^{61, 75-77}. A trained nurse, nurse practitioner or physician will collect endothelial cells from the intima of the antecubital vein of the non-dominant arm using up to 3 sterile 0.021 inch J-wires briefly advanced through a catheter. The distal portion of the wire will be transferred to a 50-ml conical tube containing a buffer solution. Cells will be recovered by centrifugation, fixed with formaldehyde, and slides will be prepared and frozen for later staining for the primary antibody of interest, a complementary fluorescent secondary Alexafluor 555 antibody (Invitrogen), VE cadherin for positive identification as endothelial cells and DAPI for nuclear integrity. The endothelial cells count per slide averages ~55 (range 25-92, estimated total of 200-736 endothelial cells per subject). More than 90% of the endothelial cells retain cellular and nuclear integrity (as determined by DAPI staining). Images will be digitally captured and analyzed using Metamorph Software (Universal Imaging Corp). Values will be reported as ratios of subject endothelial cell protein expression to human umbilical vein endothelial cell protein expression, removing the possible confound of differences in staining intensity between sessions. Using quantitative immunofluorescence, protein expression of the following proteins will be assessed:

- nitrotyrosine, as a marker of oxidative stress (Abcam)^{75, 77, 78}
- NADPH p47^{phox}, manganese superoxide dismutase (MnSOD; Chemicon Intl) and copper-zinc SOD (CuZnSOD; Upstate)^{75, 77, 78} as markers of pro and anti-oxidant signaling
- total eNOS (BD Biosciences) and eNOS phosphorylated at Ser 1177 (BD Biosciences)⁷⁹

Note: It is well establish that expression of proteins in endothelial cells obtained from venous sampling reflect individual and group differences observed in cells obtained from brachial artery sampling⁸⁰.

Risks of this procedure include: The risks associated with this procedure are those that occur with the placement of the venous catheters including small risk of pain, phlebitis, infection and blood clots (i.e., the same risks associated with venous catheterization). The risk of blood clots and infection may be slightly greater than those of an intravenous catheter due to increased manipulation of the blood vessel when compared with catheterization alone. There is also a very low likelihood that the J-shaped wire could get stuck in the vein and/or that the vein could be damaged.

Justification: This is a novel approach to evaluate the potential mechanisms (including expression of proteins modulating inflammation) by which phosphorus lowering may improve vascular function in CKD patients, with risk analogous to venous catheterization. These procedures were described originally by Colombo et al.⁵⁴ and more recently by [name] laboratory⁵⁵⁻⁵⁸. An alternative to understanding these mechanisms would be via obtaining arterial endothelial cells through an arterial line. This would be considerably more invasive, and in light of data supporting that venous endothelial cells are a good surrogate marker for arterial endothelial cells, the investigators feel this risk is not justified for the purposes of this proposal.

c) Laboratory Analyses: The majority of the laboratory measurements will be performed at the University of Colorado Clinical Laboratory using standard techniques. Samples will be collected by research nurses at the UPI Building laboratory facilities and sent to the clinical laboratory or core laboratory.

- **Serum phosphorus (Visits 1-9):** Serum phosphorus (1 mL serum) will be measured using standard methodology for study inclusion, drug titration and to determine the degree of phosphate lowering with lanthanum.
- **Follicle stimulating hormone (FSH) (Visit 1):** FSH will be measured in all women <57 years of age to confirm post-menopausal status for study inclusion (1 mL serum).
- **Comprehensive metabolic panel (Visits 1, 2, 9):** A comprehensive metabolic panel (4.5 mL plasma) will be performed for study inclusion and monthly throughout the study using standard methodology.
- **Lipid panel (Visits 2, 9):** A lipid panel (1 mL plasma) will be performed at baseline (Visit 2) and 12 weeks after lanthanum or placebo.
- **Fibroblast growth factor 23 (FGF23) (Visits 2, 9):** FGF23 (200 µL serum) will be measured pre- and post- treatment as a marker of mineral metabolism (Kainos).
- **Intact Parathyroid hormone (iPTH) (Visits 2, 9):** iPTH (4.5 mL plasma/serum) will be measured pre- and post- treatment as a marker of mineral metabolism using standard methodology.
- **25 hydroxyvitamin D (25(OH)D) (Visits 2, 9):** 25(OH)D (4.5 mL serum) will be measured pre- and post-treatment as a marker of mineral metabolism by the core laboratory (Chemilluminescence, DiaSorin Liaison).
- **1,25 dihydroxyvitamin D (1,25(OH)₂D) (Visits 2, 9):** 1,25(OH)₂D (1 mL serum) will be measured pre- and post- treatment as a marker of mineral metabolism by the core laboratory (EIA, Immunodiagnostic Systems).
- **Interleukin-6 (IL-6) (Visits 2, 5, 9):** IL-6 (1 mL plasma) will be measured pre- and post- treatment as a marker of inflammation by the CTRC core laboratory (ELISA; R&D Systems).
- **C-reactive protein (CRP) (Visits 2, 5, 9):** CRP (1 mL plasma) will be measured pre- and post- treatment as a marker of inflammation by the CTRC core laboratory (Immunoturbidimetric; Beckman Coulter).
- **Vitamin C (VITC) (Visits 2, 9):** VITC (0.5 mL plasma) will be measured before and after infusions pre- and post- treatment to assess whether the study doses change Vitamin C levels.
- **Markers of Oxidative Damage (Visits 2, 5, 9):** (1 mL serum) will be measured before and after infusions pre- and post- treatment to measure markers of oxidative damage, such as F-2 isoprostanes, by the CTRC core laboratory (ELISA, Mercodia).
- **Future studies (Visits 2, 5, 9):** For subjects signing the Informed Consent Addendum, an additional 5 mL of serum and 9 mL of plasma will be collected for future research.
- **Urine phosphorus (Visits 2, 9):** Urine phosphorus will be measured pre- and post- treatment as a marker of phosphorus excretion.
- **Urine creatinine (Visits 2, 9):** Urine creatinine will be measured pre- and post- treatment to aid in the calculation of phosphorus excretion.

Risks of this procedure include: All of the lab work will be obtained via venipuncture and the insertion of an 18 gauge cannula. The risks that are entailed in this procedure include discomfort and pain of venipuncture, failed attempt resulting in more than one attempt, bleeding upon cannula removal, and rarely thrombophlebitis (a non infectious inflammatory state of the vein typically due to prolonged cannulation). In the protocol the cannulation procedure is expected to last only for a few minutes (5-10), and the cannula will be removed immediately after obtaining the lab tests above and the endothelial cell collection. A separate cannula will then be inserted in the dorsal aspect of the hand to infuse the saline and ascorbic acid, in order to help preserve access in the arm. Subjects may be at a very small risk of anemia from the blood draws required for the assays described above. However, only the minimum amount of blood needed will be drawn and experienced research nurses/nurse practitioners will be collecting the specimens. All blood draws will be performed on the arm not designated for future vascular access for dialysis.

Justification: Please refer to the background/significance section for a detailed discussion of the importance of these serum markers with endothelial dysfunction. Patients with CKD have increased oxidative stress and inflammation compared to the general population, and lanthanum may improve vascular function by reducing oxidative stress and inflammation. These systemic blood markers will provide important insight as to the mechanisms by which phosphate lowering may improve vascular function. The other laboratory tests are necessary for subject inclusion and safety monitoring.

E. Potential Scientific Problems:

Although subject recruitment/retention are always challenging, we should be able to meet target enrollment given our location in the densely populated Denver metro area and access to the UC-Denver Nephrology Clinic at the University Hospital overseen by board-certified nephrologist, [name], and at the Denver VA Medical Center Renal Clinic, staffed by [name]. We expect few difficulties with the proposed experimental procedures and protocols as the co-investigator has employed them during her graduate training. In addition, there are currently three intervention protocols in patients with CKD being performed using all/the majority of the proposed methods (Drs. [name], [name] and [name]). We recognize that alternate phosphate binders could have been selected; however, we chose lanthanum (a) to avoid the potential side-effect of hypercalcemia that may be occur with calcium-based phosphate binders ⁸¹, (b) because calcium-based binders have not improved EDD in hyperphosphatemic CKD patients ^{49, 50}, and (c) to control for the beneficial effects that may occur with sevelamer by mechanisms other than phosphorus lowering ⁸²⁻⁸⁴. We also recognize that it would be of interest to compare to lanthanum to other phosphate binders, but given the duration and scope of the project, feel it is necessary to first compare the efficacy of lanthanum vs. placebo.

F. Data Analysis Plan:

Statistical Analysis

General: Descriptive statistics will be used to summarize continuous variables (mean, standard deviation, minima, median, and maxima) and categorical variables (N and %) for baseline characteristics by treatment group. Summaries will be provided by treatment group (lanthanum and placebo). Means and medians with variability estimates based on standard deviations or interquartile ranges will be used for graphical displays of continuous variables and histograms of percentages will be used to display the distribution of categorical variables. Highly skewed variables may be transformed prior to statistical analyses. Significance is defined with a two-sided alpha of 0.025 for the primary outcomes and 0.05 for the secondary outcomes.

Analysis Populations: The primary analysis will be intention-to-treat. The data will also be analyzed as per protocol. Subjects randomized to treatment who receive at least one drug dose and complete baseline measurements will be included in the intention-to-treat analysis, regardless of whether they adhered to the assigned intervention. In the per protocol analysis, only those subjects who were adherent to the protocol (completed all 12 weeks of drug or placebo) and completed the end of the study measurements will be included. Decisions to remove subjects from the per protocol analysis set will be made prior to breaking the treatment blind. The intention-to-treat analysis will analyze subjects as randomized; the per protocol analysis will analyze subjects as treated.

Prior to all analyses, data checks will be conducted to verify or correct assumptions about the data structure and to identify potential issues with the data being collected. This process will include range checks

to identify impossible values (e.g., age=0) and cross-tabulations identifying relations between key variables. Differences between groups at baseline will be assessed by unpaired t-tests and changes in response to lanthanum vs. placebo by ANOVA for repeated measures. In the case of a significant F-value, post hoc tests will be performed using the Newman-Keuls method. The influence of changes in 2° outcomes (blood pressure, mechanistic variables, etc.) on changes in 1° outcomes in response to lanthanum will be examined by multiple linear regression. Potential confounders, such as changes in other characteristics that are known to influence vascular function (e.g. body mass, blood pressure) will be handled using ANCOVA. Alpha for the two primary endpoints will be set at 0.025 while there will be no adjustment for secondary outcomes as they will be considered exploratory.

G. Summarize Knowledge to be gained:

The findings from the proposed research should provide important new information regarding the potential benefits of phosphorus lowering upon the reduction of vascular dysfunction in patients with CKD. It should also provide important insight into the mechanisms involved in the modulation of EDD by elevated phosphorus. Together, this information will add to the knowledge of how to prevent and treat vascular dysfunction in patients with CKD.

H. References:

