Experimental Design (Figure 1). A 12-week randomized, placebo-controlled, double-blind design study with lanthanum (starting dose of 1,500-3,000 mg/day according to baseline serum phosphorus; up-titrated monthly as needed based on serum phosphorus) will be conducted. After providing informed consent, subjects will undergo screening prior to study start. Subjects who meet inclusion criteria will have baseline measurements performed as described below. Measurements will be made under supine, overnight fasted (water only) conditions. Patients will then be randomly assigned to receive either lanthanum or placebo (see dosing below). Allocation to the active drug versus placebo group will be random, and a stratification process will be used on the basis of baseline FMD_{BA} of <4% and $\geq 4\%$ to protect against a baseline imbalance that would not

be well handled by other statistical procedures. With counseling and adherence monitoring from a nurse, subjects will maintain their baseline diet throughout the study, including intake of phosphate of <1,000 mg/day. Measurements will then be repeated after 12 weeks. The investigators involved in the acquisition and analysis of key outcomes will be blinded to the treatment assignment of the subjects as well as serum phosphorus levels.

Figure 1:

Subjects will come to the lab at the UPI Building on 9 separate occasions:

- **Session 1:** Screening measurements, complete 3 day diet record
- **Session 2:** Baseline measurements
 - Resting arterial blood pressure and blood sampling of circulating markers (see below)
 - Venous endothelial cell collection (for subsequent protein measurements)
 - FMD_{BA} (endothelium-dependent dilation) and aortic PWV (arterial stiffness), with and without acute inhibition of oxidative stress via systemic i.v. infusion of ascorbic acid [vitamin C])
 - Endothelium-independent dilation (EID) to sublingual nitroglycerin
 - Begin study treatment (lanthanum or placebo)
- **Sessions 3-8:** Weekly/monthly check-in (see below)
- **Session 9:** Identical to Session 2 (note: subjects will not take a dose the a.m. prior to testing session)
 - **Subjects will also complete a second 3 day diet record**

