- c) ***Blinding:*** The investigators and patients will remain blind to the study intervention, as the lanthanum and placebo will be identical. A nurse at the UPI Building lab will be responsible for administering the pills, which will be stored in a locked cabinet on site. A professional research assistant will be unblinded and will manage the study drug records and interact directly with the nursing staff for administration of the study drug. The investigators will be blinded to laboratory results, and the research assistant will monitor laboratory results for safety and inform the investigator if necessary.
- d) ***Drug accountability:*** Pill counts will be assessed weekly during the 1st month and then monthly to document subject adherence.
- e) ***Withdrawal from study:*** Withdrawal will be done at the patient's request, IRB request, or if there is a medical rationale for discontinuation as determined by the principal investigator.

Safety monitoring

The patients will be instructed to call the PI or research coordinator with any subjective complaints, in addition, abnormal labs will be reported to the PI immediately, who will determine if the study drug needs to be discontinued. The following are reported adverse events of the study drugs and the monitoring plan:

a) Lanthanum. The safety profile of lanthanum has been studied in over 5200 subjects in completed clinical trials. The most common adverse reactions for lanthanum are gastrointestinal events, such as nausea, vomiting, and abdominal pain and they generally abate over time with continued dosing. In end-stage renal disease patients receiving 4-6 weeks of treatment with lanthanum the incidence of nausea was 11% (vs. 5% placebo), vomiting 9% (vs. 4%) and abdominal pain 5% (vs. 0%). Lanthanum may reduce calcium absorption and result in hypocalcemia (~5%, same incidence as active comparator group). The following additional adverse reactions have been identified in during post-approval use of lanthanum: constipation, dyspepsia, allergic skin reactions, hypophosphatemia, and tooth injury (incidence not known). Lanthanum may decrease bioavailability of cationic antacids, quinolone antibiotics or levothyroxine.

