There have been reports of serious cases of gastrointestinal obstruction, ileus, and fecal impaction reported in association with lanthanum, some requiring surgery or hospitalization. Risk factors for gastrointestinal obstruction identified from post-marketing reports include alteration in gastrointestinal anatomy (e.g., history of gastrointestinal surgery, colon cancer), hypomotility disorders (e.g., constipation, ileus, diabetes) and concomitant medications (e.g., calcium channel blockers). Some cases were reported in patients with no history of gastrointestinal disease.

Hypophosphatemia has been reported only in post-marketing surveillance. The risk of hypophosphatemia is very low. Clinically significant (causing symptoms) hypophosphatemia associated with the use of lanthanum carbonate has not been reported.

Safety measures will include: lanthanum dose titration and close monitoring of serum phosphate (as described above) to avoid severe hypophosphatemia, excluding patients at high risk for gastrointestinal events or current bowel obstruction, ileus and fecal impaction, repeatedly emphasizing to patients the importance of chewing tablets completely to reduce the risk of serious adverse gastrointestinal events such as those described above. Patients will also be instructed to take concomitant drugs at least one hour before or four hours after lanthanum to avoid potential interactions, and blood levels of concomitant drugs with a narrow therapeutic range will be monitored if deemed appropriate by [name].

Patient Stopping Criteria:

- Withdrawal of informed consent (subject's decision to withdraw for any reason)
- Any clinical adverse event (AE), laboratory abnormality or intercurrent illness which, in the opinion of the investigator, indicates that continued participation in the study is not in the best interest of the subject
- Loss of ability to freely provide consent through imprisonment or involuntary incarceration for treatment of either a psychiatric or physical (e.g., infectious disease) illness
- Inability to comply with protocol
- Use of an investigational therapy or device other than study medication
- Significant non-compliance with protocol (ie, procedures, assessments, medication, etc.)
- Hypocalcemia that does not resolve with decreased dosage of study drug
- Hypophosphatemia (<2.5 mg/dL) that does not resolve with decreased dosage of study drug
- Hospitalization for gastrointestinal obstruction, ileus, and fecal impaction

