- Serious acute hypersensitivity reactions to investigational drug
- Any major cardiovascular event such as myocardial infarction, stroke, unstable angina, thromboembolic event, or a clinically significant deterioration of a baseline cardiovascular condition.

Study Stopping Criteria:

The study may be stopped if:

- The data show a significantly increased risk of serious adverse effects in one of the treatment groups.
- Interim efficacy analyses show significant treatment benefits or futility in the intervention group. The interim efficacy analyses are based on pre-specified stopping boundaries for the primary endpoint of the study which preserve the study wide Type I error rate.

- It becomes clear that successful completion of the study is not feasible (e.g. there is an excess of patient dropout, missing data, lack of recruitment etc).

Standard medical treatment for all subjects/concomitant medications includes:

All subjects must be on a stable anti-hypertensive, diabetic and lipid lowering regimen for at least one month prior to inclusion.

a) Control of hypertension with anti-hypertensives with goal blood pressure less than 130/80 mm/Hg. Medication choice includes angiotensin converting enzyme inhibitor/angiotensin receptor blocker as first line agent, diuretic as second line agent, calcium channel blocker as third line agent, and beta blocker as fourth line agent (unless patient has known CVD and needs to be on a beta blocker regardless of blood pressure). b) Diabetes will be treated as needed to goal HbA1C of 7.0%. c) Control of hyperlipidemia with statins to goal of low density lipoprotein cholesterol (LDL-C) <100 mg/dL and total cholesterol levels to less than 200 mg/dL. d) Smoking cessation counseling. e) Control of anemia following the latest recommendation from the National Kidney Foundation. f) Control of hyperphosphatemia with phosphorus binders and down titration of the intervention as described above to a goal phosphorus < 4.6 mg/dL.

Data Collection

Screening Measures and Potential Confounders:

Medical History, Physical Examination and Blood Chemistries. Subjects will report fasted for assessment of serum phosphorus and a standard blood chemistry analysis including a metabolic panel (with creatinine/calcium), blood count, lipid panel and follicle stimulating hormone (women only), then undergo a medical history and physical examination.

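### The parent protocol gives two schedules for the metabolic panel, and under one of them the hypocalcaemia stopping criterion has no calcium result to act on before week 12

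*Combined protocol and SAP*

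**What the plan says.** All references are to the parent protocol (13-0328) unless stated.

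- **IV.D, Secondary (Exploratory) Outcomes, c) Laboratory Analyses.** The bullet opens "Comprehensive metabolic panel (Visits 1, 2, 9". Its text then says the panel "will be performed for study inclusion and monthly throughout the study using standard methodology".
- **IV.C, Data Collection, Screening Measures.** The panel is identified as the source of calcium: "a standard blood chemistry analysis including a metabolic panel (with creatinine/calcium".
- **IV.C, Experimental Design.** The trial is "A 12-week randomized, placebo-controlled, double-blind design study with lanthanum". Session 1 is screening. Session 2 is baseline, and its last item is "Begin study treatment (lanthanum or placebo". Sessions 3-8 are described only as "Weekly/monthly check-in (see below". Session 9 repeats the baseline session at 12 weeks.
- **IV.C, Safety monitoring, a) Lanthanum.** Hypocalcaemia is a named risk: "Lanthanum may reduce calcium absorption and result in hypocalcemia (~5%, same incidence as active comparator group".
- **IV.C, Patient Stopping Criteria.** One criterion is "Hypocalcemia that does not resolve with decreased dosage of study drug".

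**The concern.** The two halves of one bullet describe different schedules, and nothing says which governs. The difference falls entirely in the treatment period. The visit list places panels before treatment and at its end, whereas the monthly wording also places them in between.

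A stopping criterion depends on which is followed. It has three steps: a low calcium is found while the subject is taking study drug, the dose is decreased, and calcium is measured again. If staff follow the visit list, the first calcium after treatment starts comes when the 12 weeks are complete. A written safety criterion would then have no scheduled data during the period it is meant to cover, for a risk the protocol itself lists.

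**Working it through.** There is no power or alpha figure to reproduce. The check counts scheduled panels under each statement and compares the count with what the criterion needs.

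**Inputs.** Treatment lasts 12 weeks and begins at the end of Session 2. There are 8 - 3 + 1 = 6 check-in sessions (3 to 8). The end-of-study session is Session 9. I take Visit n in the laboratory list to be Session n in the design section; both run from 1 to 9. I take a month as about four weeks, which matches the four-weekly titration after the initial period.

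| Schedule followed | Session 1 (screening) | Session 2 (baseline, before first dose) | Sessions 3-8 (check-ins) | Session 9 (week 12) |
|---|---|---|---|---|
| Visit list | 1 | 1 | 0 | 1 |
| Monthly wording | 1 | not stated | about 2 | 1 |

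**Visit list.** Of Visits 1, 2 and 9, none lies between 3 and 8. That is 0 of 6 check-in sessions with a panel.

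**Monthly wording.** 12 / 4 = 3 panels after the start of treatment, at about weeks 4, 8 and 12. The last coincides with Session 9, leaving 3 - 1 = 2 during the check-in period.

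**What the criterion needs.** At least two calcium results: one during dosing, and one after a dose decrease.

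- Visit list: no result before week 12 and one at week 12. The decrease and the repeat cannot follow within the parent trial.
- Monthly wording: a result near week 4, a decrease and a repeat near week 8 is a possible sequence, as is week 8 followed by week 12. The criterion can operate.

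**Other sources of calcium in the readable text.** I found none scheduled at Sessions 3-8. Serum phosphorus is listed at every visit, and IL-6, CRP and the oxidative damage markers are listed at Visit 5, so these lists do show draws during treatment where they are intended. For its subjects recruited outside the parent trial, the balance substudy protocol (15-0834) lists the metabolic panel at all of Visits 1-7.

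**The case against.** The strongest reply is that the monthly wording is plainly what was meant. IV.A says chemistries will be followed through the study for safety. The Blinding and Safety monitoring text has a research assistant watching laboratory results and abnormal values going to the investigator at once. The justification under Laboratory Analyses says the remaining tests serve eligibility and safety. The bullet's own sentence makes the stopping criterion workable. The laboratory list is also loosely drafted elsewhere: IL-6 and CRP are listed at Visits 2, 5 and 9 but described as pre- and post-treatment measurements.

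Much of this stands. These statements favour the monthly reading. But none names calcium or a visit, and reporting of abnormal values applies only to tests that are drawn. They do not remove the conflict.

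Four stronger readings are tempting, and the documents do not support them:

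- **That the visit list gives no calcium on treatment at all.** Session 9 has a panel at week 12, with only that morning's dose withheld. Drop-outs are to have an end-of-study visit with the Session 9 measurements. Subjects who go on to the balance substudy stay on their dose and have panels at its Visits 2 and 3. The gap is between the start of treatment and the end-of-study visit.
- **That the ~5% rate, multiplied by the number of lanthanum subjects, shows how often the criterion would be needed.** The rate is for any hypocalcaemia, follows data from end-stage renal disease, and has no definition or placebo rate. The criterion covers only cases that persist after a dose decrease, a subset whose rate is not given.
- **That phosphorus is the only test with a clear on-treatment visit list.** The Visit 5 markers are listed too.
- **That the case report form will follow the visit list, so calcium data will be lost.** The documents do not say how the form derives from the laboratory list. They say only that the whole research team defines the data dictionary iteratively.

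**Conclusion.** The contradiction is real and should be corrected. Its size is 0 scheduled calcium results at the six check-in sessions on the visit list, against about 2 on the monthly wording. Under the visit list, the hypocalcaemia criterion cannot operate within the parent trial, apart from the limited exceptions of early drop-outs' end-of-study visit and continuation into the balance substudy. Under the monthly wording it can.

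This is an internal inconsistency with a safety consequence. It does not touch the primary outcomes, the sample size or the significance level, and it is not evidence that calcium went unmonitored in practice.

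The conclusion assumes that visit and session numbers correspond, that a month is about four weeks, and that the design figure, which was not readable, does not settle the schedule.

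**What to change.** Reconcile the visit list, the monthly wording and the hypocalcaemia stopping criterion into one schedule. State it once in IV.D c) Laboratory Analyses and repeat it under Sessions 3-8 in IV.C, Experimental Design. The criterion and the schedule should agree on which calcium results the criterion uses. Which schedule is right is for the sponsor and investigator.

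The cost is a short edit in two places. If the monthly schedule is kept, each panel takes 4.5 mL of plasma, so two panels at check-ins add 2 x 4.5 = 9 mL per subject, at visits where blood is already drawn for phosphorus. That is small, though the protocol undertakes to draw only the minimum blood needed, so the volume should be counted.
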